### Secondary Outcomes

Continuous secondary outcomes will be compared between treatment groups using a t-test.

Categorical secondary outcomes will be compared between treatment groups using a Chi-square or Fisher's exact test as appropriate to the sparseness of the data.

The analysis is intention to treat and significance testing will be two-tailed at  $\alpha = 0.05$  with no adjustment made for multiple comparisons.

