9.1 Sample Size and Stopping Rules for Primary Outcome

The primary outcome is intention-to-treat 90-day all cause in-hospital mortality, where in-hospital includes both study and discharge hospitals (i.e. transfer hospitals or LTAC). Subjects who are discharged home (defined as residence prior to admission) prior to day 90 will be assumed to be alive at day 90.

Sample size is based on a comparison of binomial proportions with an overall two-sided alpha level of 0.05 and power of 0.90. With 15% mortality rate in liberal fluid group and 10.5% mortality rate in the restrictive group, maximum required total sample size is 2320 subjects.

The presumed 15% mortality rate in the liberal fluid group is based on several recently published clinical trials (Process [2], ARISE [3], Promise [4]).

This trial will stop for efficacy of either the restrictive or liberal fluid strategy arm, or futility. The study is designed with a symmetric group sequential t^4 alpha error spending function and a symmetric non-binding t^4 beta error spending function, where t is the information time, defined as the ratio of the effective sample size at the time of the look to the eventual sample size.

We plan to have two interim analyses and one final analysis that will be approximately evenly spaced. However, the scheduling of the DSMB meetings may alter this schedule.

Tables 1 and 2 present the stopping boundaries at each of the two interim analyses if they are equally spaced. The tables present stopping boundaries as either a one-sided p-value or an observed mortality difference. Table 3 presents the probability of stopping at each stage under the null (no effect of fluid) and alternative (restrictive fluid reduces mortality from 15% to 10.5%) hypotheses respectively.

Table 1. Stopping Boundaries: One Sided P Values

Stage	Sample Size	Lower Efficacy	Lower Futility	Upper Futility	Upper Efficacy
1	773	0.0003086	.	.	0.99969
2	1547	0.00479	0.27413	0.72587	0.99521
3	2320	0.02361	0.02361	0.97639	0.97639

Table 2. Stopping Boundaries: Mortality Differences

Stage	Sample Size	Lower Efficacy	Lower Futility	Upper Futility	Upper Efficacy
1	773	-0.08194	.	.	0.08194
2	1547	-0.04384	-0.01016	0.01016	0.04384
3	2320	-0.02742	-0.02742	0.02742	0.02742

Table 3. Cumulative Stopping Probabilities

Stage	Stop: Reject Null Given Null	Stop: Accept Null Given Null	Stop: Reject Null Given Alternative	Stop: Accept Null Given Alternative
1	0.00062	0.00000	0.06136	0.00000
2	0.00988	0.45174	0.52878	0.01919

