## 1.9 Secondary Endpoints

1. 28-day organ support free days (alive and without mechanical ventilation, new renal replacement or vasopressors; vasopressors prior to 48 hours excluded)
2. 28-day ventilator free days
3. 28-day renal replacement free days (new renal replacement therapy)
4. 28-day vasopressor free days (vasopressors prior to 48 hours excluded)
5. 28-day ICU free days
6. 28-day hospital free days to discharge home
7. Initiation of mechanical ventilation to day 28
8. Initiation of renal replacement therapy to day 28
9. Change in creatinine-based KDIGO stage between baseline and 72 hours
10. Change in SOFA score between baseline and 72 hours
11. 90-day all-cause mortality
12. Development of ARDS within 7 days
13. New onset atrial or ventricular arrhythmia to day 28
14. Additional secondary safety endpoints:
  - a. New intubation through day seven
  - b. New mechanical ventilation through day seven
  - c. Ventricular arrhythmias in first 24 hours
  - d. New renal replacement therapy through day seven
  - e. New ARDS through day seven
  - f. ICU admission through day seven
  - g. Central venous line insertion through day three
  - h. Vasopressor infusion through peripheral venous catheter
  - i. Line complications of central venous catheter placement
  - j. Line complications
  - k. More than three line complications among patients with a line complication
  - l. Site extravasation to day 28 from peripheral venous catheter infusion
  - m. New ventilation and oxygen use in first 24 hours
  - n. Adverse events

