### **1.11 Sample Size/Interim Monitoring**

1. Randomization 1:1; two-sided alpha 0.05.  
A total of 2320 patients are needed to detect a 4.5% absolute mortality difference between treatment groups with 90% power assuming 15% mortality in the liberal fluids group. The principal analysis will be intent-to-treat, based upon randomization assignment.
2. There will be a protocol feasibility assessment phase at the approximately 100-patient mark, and then after approximately 100 enrolled patients are available after any protocol changes for 2 more evaluation assessments. Aggregate data blinded to outcomes will be used to assess patient accrual, treatment protocol compliance, and separation of intravenous fluid and/or vasopressor administration. Protocol adjustments may be made at each of these patient marks to optimize the protocol. The study may be halted during the feasibility assessment phase for failure to meet pre-specified stopping guidelines
3. Trial progress will be evaluated by an independent Data and Safety Monitoring Board (DSMB) to determine whether the study should stop for superiority of either the liberal or restrictive fluid strategies; or, for projected trial futility. (See Appendix B) There will be two interim analyses and a final analysis conducted when approximately each successive 1/3 of the patients have been enrolled.

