**10. Change in SOFA score between baseline and 72 hours**

We will calculate the SOFA score upon enrollment and at 72 hours using clinically available data. If a value is not available at baseline, it will be assumed to be normal. At the 72 hours assessment, if a value is missing then we will carry forward the closest previously known value. If a patient is intubated or heavily sedated at either 0 or 72 hours, the GCS will be omitted when calculating the change in score. If a patient was on renal replacement therapy prior to presentation, then the renal dysfunction component to the SOFA score will be omitted as well.

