#### 4. Baseline Characteristics

1. Demographics – Age, Gender, Ethnicity, Race
2. Primary source of infection
3. Co-Morbidities – Charlson, BMI, Pre-hospital level of care
4. Location at time of randomization
5. Illness severity – SOFA (Total and components), mechanical ventilation, ARDS, total pre-randomization fluid input, vasopressor use and infusion rate prior to and at randomization, vital signs, WBC, lactate

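### Change in SOFA is compared by an unadjusted t-test although enrolment SOFA is collected; adjusting for it would be a free gain in precision, of a size the documents do not allow one to fix

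*SAP*

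**What the plan says.** SAP section 1.9 lists as item 10 "Change in SOFA score between baseline and 72 hours". Section 2.2, item 10, defines it: "We will calculate the SOFA score upon enrollment and at 72 hours using clinically available data". The same item scores components missing at baseline as normal and fills gaps at 72 hours with the nearest previous value. It leaves GCS out of the change if the patient is intubated or heavily sedated at either time, and leaves out the renal component for patients already on renal replacement therapy before presentation.

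For the analysis, SAP section 5 (Secondary Outcomes) says: "Continuous secondary outcomes will be compared between treatment groups using a t-test". It continues: "The analysis is intention to treat and significance testing will be two-tailed at" 0.05, without multiplicity adjustment. No covariate is named. The SAP does not list which endpoints count as continuous, but change in SOFA is naturally read as one of them.

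SAP section 4 includes "SOFA (Total and components" among the baseline characteristics. Enrolment SOFA enters a model only through SAP section 3, item 7 (quartiles), and the Secondary Analysis by Subgroups paragraph of section 5. Those are subgroup analyses; the main comparison does not use it.

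**The concern.** Taking the difference between two scores and comparing it by t-test fixes the slope on baseline at 1. When the true slope is smaller, part of the baseline noise is carried into the comparison. A regression that estimates the slope removes that part, using data the trial already holds.

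One feature of this trial makes the slope worth estimating. A component missing at baseline is scored as normal. If it is then measured as abnormal at 72 hours, it appears as worsening, and the change score carries that error at full weight. This rule would tend to lower the correlation between the two scores; carrying values forward to 72 hours would tend to raise it. The documents do not show which effect dominates.

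At stake is the precision of the trial's estimate of early organ-failure recovery. The documents give no power, SD or target difference for SOFA, so spare precision cannot be taken for granted.

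**Working it through.** **The plan's own figure.** The only sample size that bears on this endpoint was set for mortality (Protocol 9.1): "With 15% mortality rate in liberal fluid group and 10.5% mortality rate in the restrictive group, maximum required total sample size is 2320 subjects". For a fixed design with two-sided alpha 0.05 and 90% power, the number per group is [1.960·√(2·0.1275·0.8725) + 1.282·√(0.15·0.85 + 0.105·0.895)]² / 0.045² ≈ 1153, or 2306 in total. Simulating the stated three-stage boundaries at 2320 gives power 0.898, against 0.89765 in Protocol Table 3. The stated size is reproduced, but it says nothing about SOFA.

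**Inputs.** From the documents: t-test on the change (SAP 5), both scores measured (SAP 2.2), 1:1 allocation (SAP 1.11), at most 2320 patients. Assumed, because the documents do not give them: ρ, the correlation between baseline and 72-hour SOFA, taken as 0.3 to 0.7; and k = SD(72 h)/SD(baseline), taken as 1 and then varied from 0.8 to 1.5.

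**Formula.** With baseline variance 1:

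- variance of the change: 1 + k² − 2kρ
- residual variance after adjusting for baseline: k²(1 − ρ²)
- share of information lost by not adjusting: 1 − k²(1 − ρ²)/(1 + k² − 2kρ) = (1 − kρ)²/(1 + k² − 2kρ)

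This share is the squared correlation between the change and the baseline score. It cannot be negative, and it is zero when kρ = 1. With k = 1 it reduces to (1 − ρ)/2.

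**Equal SDs (k = 1).** The standard error ratio is √(2/(1 + ρ)). The effective number is 2320·(1 + ρ)/2, if all 2320 are analysed. The last column is Φ(3.2415·√((1 + ρ)/2) − 1.960), the power of the t-test when the adjusted analysis has 90%.

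| ρ | Information lost | SE ratio, t-test to adjusted | Effective N of 2320 | t-test power if adjusted has 90% |
|---|---|---|---|---|
| 0.3 | 35% | 1.24 | 1508 | 74% |
| 0.5 | 25% | 1.15 | 1740 | 80% |
| 0.7 | 15% | 1.08 | 1972 | 85% |

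Simulation with 2320 patients and 3000 runs gave adjusted-to-unadjusted variance ratios of 0.63, 0.77 and 0.86, against 0.65, 0.75 and 0.85 from the formula.

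**Unequal SDs.** Information lost:

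| k | ρ = 0.3 | ρ = 0.5 | ρ = 0.7 |
|---|---|---|---|
| 0.8 | 50% | 43% | 37% |
| 1.0 | 35% | 25% | 15% |
| 1.2 | 24% | 13% | 3% |
| 1.5 | 13% | 4% | 0.2% |

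For example, at k = 0.8 and ρ = 0.3: (1 − 0.24)²/(1 + 0.64 − 0.48) = 0.5776/1.16 = 0.498. At k = 1.5 and ρ = 0.7: (1 − 1.05)²/(3.25 − 2.10) = 0.0025/1.15 = 0.002.

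These figures assume that the covariate is the same score that enters the change. Where item 10 drops a component from the change but not from the covariate, the gain is still the squared correlation of change and covariate, but its value will differ somewhat.

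**The case against.** Much of the case for leaving the plan alone is sound, and it limits the point.

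- *Validity.* The t-test on change is unbiased under randomisation. It meets the standard the SAP sets in its Null Hypothesis paragraph, namely correct comparison-wise type I error under the global null. A reader might infer that regression to the mean or chance imbalance biases the comparison. It does not: regression to the mean acts on both arms alike, and chance imbalance is already part of the standard error. At full size the standard error of a baseline difference is only 2/√2320 ≈ 0.04 SD. With equal SDs, an imbalance d shifts the expected difference in change by −(1 − ρ)d.
- *Size.* A reader might take 15–35% as an established loss. It rests on assumed values of ρ and on equal SDs. Nor is the adjusted variance strictly smaller at every correlation below 1: at k = 1.5 and ρ = 0.67 the two analyses are equally precise.
- *Consequence.* This is one of thirteen numbered secondary endpoints ahead of the safety list. As an illustration, with an assumed change-score SD of 4 points and all 2320 analysed, the standard error is about 0.17, against 0.14 after adjustment at ρ = 0.5. No conclusion is shown to turn on that difference.
- *DSMB reports.* Protocol 7.2 sends changes in SOFA to the DSMB quarterly. It does not say that those reports use the SAP's t-test, so no harm to safety monitoring follows from the text.
- *A trap in adjusting.* Matching the covariate's components to those in the change would make the baseline covariate depend on intubation or sedation at 72 hours. That is a post-randomisation state which the strategy may affect, and the usual guarantee for adjustment would no longer hold. This is a good reason against that form of adjustment. It does not count against using a covariate fixed before randomisation.

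The subgroup models with SOFA quartiles do not fill the gap, because they do not alter the main comparison.

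**Conclusion.** The point stands as one of efficiency. The planned comparison of change in SOFA is valid, but asymptotically it is never more precise than one adjusted for enrolment SOFA. The loss is (1 − kρ)²/(1 + k² − 2kρ). It equals 35%, 25% and 15% at ρ = 0.3, 0.5 and 0.7 if the two SDs are equal, and runs from about 0% to 50% for SD ratios of 0.8 to 1.5 over the same ρ. The documents supply neither quantity, so no single figure can be claimed. The result also rests on 1:1 allocation and a covariate fixed before randomisation. The change should be made because it costs almost nothing. It affects one secondary endpoint and leaves the primary outcome and the sample size of 2320 untouched.

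**What to change.** Add to SAP section 5, Secondary Outcomes:

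> Change in SOFA, as defined in 2.2 item 10, is compared by linear regression of the change on treatment and enrolment SOFA score computed from pre-randomisation values only; the t-test is kept as a sensitivity analysis.

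Two details need stating with it. First, the covariate must not be defined by intubation or sedation status at 72 hours. Component omissions that depend only on pre-randomisation status are acceptable. Second, Protocol 7.1 lets background values be measured up to 24 hours when none is available from the preceding 24 hours. The restriction to pre-randomisation values is therefore needed, with the existing normal-value rule covering any component that is then missing.

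Regressing the change, rather than the 72-hour score, keeps the endpoint as defined. Where the components are identical, both models give the same treatment estimate. The cost is one sentence, the short definition of the covariate and one extra model term, with no new data. This does not settle how SOFA is scored for patients who die before 72 hours; item 10 does not address that, and it is a separate matter.

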### Process of Care Metrics

The analysis of the process of care metrics will be similar to that of the secondary outcomes.

The analysis is intention to treat and significance testing will be two-tailed at  $\alpha = 0.05$  with no adjustment made for multiple comparisons.

### Adverse Events

Adverse events will be analyzed using weighted Poisson regression with non-serious events weighted by one and serious events weighted by two. Events rather than patients will be the unit of analysis. Adverse events will be grouped and analyzed separately by MedDRA system organ classes.

The analysis is intention to treat and significance testing will be two-tailed at  $\alpha = 0.05$  with no adjustment made for multiple comparisons.

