4.7 Randomization

After obtaining a signed and dated informed consent from the subject or the subject's legal authorized representative (LAR), we will randomize subjects via the coordinating center web based randomization system. Each research coordinator will have a unique Personal Identification Number (PIN) to access the randomization system. Each subject will receive a computer-generated study ID number and study arm assignment to either the restrictive or liberal treatment arm. An emailed confirmation will be sent to the study site. Randomization will be stratified by the enrolling institution.

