8.1 Subject Accrual

The maximum sample size for the study is 2,320 subjects. We estimate that sample size is achievable in a timely fashion if we enroll an average of 1 patient/site/month, distributed across 50 enrolling sites. For the feasibility assessment phase, if the enrolling sites achieve >70% of this rate (> 0.7 patients/site/month), then the feasibility guideline for patient accrual will have been met. A site will be defined as “started” when the site indicates that they have begun

screening, and the #patients/month/sites will be calculated as the number of patients enrolled across all sites, divided by sum of the screening months among the site, and number of sites. A calendar month is defined by the number of days passed since the initiation of screening, divided by 30. If a site withdraws from the study, then they will stop contributing patients and calendar months.

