13.1 Safety Monitoring

Assuring patient safety is an essential component of this protocol. Each participating investigator has primary responsibility for the safety of the individual participants under his or her care. The Investigators will determine daily if any adverse events occur during the period from enrollment through **study day 6** (five days after completion of the study fluid protocol) or Hospital discharge, whichever occurs first.

The following adverse events will be collected in the adverse event case report forms:

- Serious adverse events
- Non-serious adverse events that are considered by the investigator to be related to study procedures or of uncertain relationship (Appendix G)

A clinical trial adverse event is any untoward medical event associated with study procedures, whether or not it is considered related to the study procedures.

After randomization, adverse events must be evaluated by the investigator. If the adverse event is judged to be reportable, as outlined above, then the investigator will report to the CCC their assessment of the potential relatedness of each adverse event to protocol procedure via electronic data entry. Investigators will assess if there is a reasonable possibility that the study procedure caused the event, based on the criteria outlined in Appendix G. Investigators will also

consider if the event is unanticipated or unexplained given the patient's clinical course, previous medical conditions, and concomitant medications.

Determining whether a treatment is causally related to the development of increased oxygen requirements is a challenge, as it is difficult for a clinician to reliably discern hydrostatic from non-hydrostatic pulmonary edema. Furthermore, increased hypoxia and/or need for additional respiratory support may be due to disease progression (eg early phases of ARDS) or a fluid bolus and this is also difficult to discern. We will not consider the study endpoints of use of high-flow nasal cannula, non-invasive ventilation, or endotracheal intubation as AEs unless the events are judged by the investigator to be related to study procedures (see Appendix G2).

If a patient's treatment is discontinued as a result of an adverse event, study site personnel must report the circumstances and data leading to discontinuation of treatment in the adverse event case report forms.

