Serious adverse events will be collected during the first **6 study days** or until ICU discharge, whichever occurs first, regardless of the investigator's opinion of causation. Thereafter, serious adverse events are not required to be reported unless the investigator feels the events were related to either study drug or a protocol procedure.

Appendices

[figure not shown]
A. Protocol Schema

¹ extreme hypovolemia defined as IVC < 5mm, empty left ventricle; Volume responsiveness by any measure > 30%

[figure not shown]
A.1 Liberal Protocol (follow for 24 hours)

Liberal Arm Flow Chart (follow for 24 hours)

Fluid Liberal Flowchart

A.2 Restrictive Protocol (follow for 24 hours)

^AEpinephrine suggested, but not mandated, as second vasopressor

^BNorepinephrine 20mcg/min or 0.25 mcg/kg/min

^CDefined as: maximal IVC diameter < 5mm; or Empty left ventricle on echo (e.g. left-ventricular end-diastolic area index < 5.5 cm²/m² BSA) or Substantial volume responsiveness defined as stroke volume increase > 30% in response to a passive leg raise, fluid challenge, or positive pressure breaths

B. Data and Safety Monitoring Board

The principal role of the DSMB is to assure the safety of patients in the CLOVERS trial. They will regularly monitor data from this trial, review and assess the performance of its operations, and make recommendations to the NHLBI with respect to:

- Review of adverse events
- Interim results of the study for evidence of efficacy or adverse events
- Possible early termination of the trial because of early attainment of study objectives, safety concerns, or inadequate performance
- Possible modifications in the clinical trial protocol
- Performance of individual centers

Two interim analyses will be conducted at approximately 33% and 66% target enrollment accrual.

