- Related or possibly related to participation in the research, in this guidance document, possibly related means there is a reasonable possibility that the incident, experience, or outcome may have been caused by the procedures involved in the research;
- Suggests that the research places subjects or others at a greater risk of harm (including physical, psychological, economic, or social harm) than was previously known or recognized.

G2. Determining relationship of adverse events to procedures

Investigators will be asked to grade the strength of the relationship of an adverse event to study procedures as follows:

- **Definitely Related:** The event follows: a) A reasonable, temporal sequence from a study procedure; and b) Cannot be explained by the known characteristics of the patient's clinical state or other therapies; and c) Evaluation of the patient's clinical state indicates to the investigator that the experience is definitely related to study procedures.
- **Probably or Possibly Related:** The event should be assessed following the same criteria for "Definitely Associated". If in the investigator's opinion at least one or more of the criteria are not present, then "probably" or "possibly" associated should be selected.
- **Probably Not Related:** The event occurred while the patient was on the study but can reasonably be explained by the known characteristics of the patient's clinical state or other therapies.
- **Definitely Not Related:** The event is definitely produced by the patient's clinical state or by other modes of therapy administered to the patient.
- **Uncertain Relationship:** The event does not meet any of the criteria previously outlined.

[figure not shown]
G3. Clinical outcomes that may be exempt from adverse event reporting

Study-specific clinical outcomes of sepsis, as outlined in Sections 3.8.1 and 3.8.2 (Primary and Secondary Outcomes) and Section 6.3 (Assessments During the Study) are exempt from adverse event reporting unless the investigator deems the event to be related to the study procedures (or of uncertain relationship) or if the event leads to discontinuation of study procedures. The following are examples of events that will be considered study specific clinical outcomes

- Death not related to the study procedures.

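### The adverse-event model counts each serious event twice but states no variance; with the Poisson model's own standard error and unscaled weights, class-level tests exceed their nominal 5% once counts are moderate

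*SAP*

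**What the plan says.** The Adverse Events part of SAP section 5 sets the method: "Adverse events will be analyzed using weighted Poisson regression with non-serious events weighted by one and serious events weighted by two". It adds that "Events rather than patients will be the unit of analysis" and that "Adverse events will be grouped and analyzed separately by MedDRA system organ classes". Tests are two-tailed at 0.05 with no multiplicity adjustment. Neither there nor elsewhere do the documents name a sandwich variance, a scale parameter or a permutation test for this model. For the primary outcome, by contrast, the SAP does name its standard error (Greenwood's).

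The serious share of events is not given, and the collection rules pull it in both directions:

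- Protocol 13.1 restricts the non-serious events collected to "Non-serious adverse events that are considered by the investigator to be related to study procedures or of uncertain relationship".
- Protocol 13.2 collects serious events in the early window "regardless of the investigator's opinion of causation". Together with 13.1, this raises the serious share.
- Protocol Appendix G3 says that many sepsis outcomes "are exempt from adverse event reporting unless the investigator deems the event to be related to the study procedures", or of uncertain relationship, or the event ends study procedures. This lowers the serious share.

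**The concern.** A Poisson model takes the variance of a count to equal its mean. Giving an event weight two doubles its contribution to the mean but quadruples its contribution to the variance. Unless the variance is corrected, the model treats one serious event as two independent ones, and its intervals are too narrow.

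The trial is not blinded, and its two arms carry different expected harms: fluid overload in one, ischemia and arrhythmia in the other (Protocol 11.1). A class-level result that crosses 0.05 only because serious events were double-counted could be read as harm from one strategy.

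**Working it through.** **Inputs.** From the SAP: weights 1 and 2, two-sided level 0.05, 1:1 allocation. Maximum sample size 2320, so 2320/2 = 1160 patients per arm. Assumed, because the documents give no figure: serious share p = 0.05, 0.1, 0.2, 0.5 or 1, and the number of events per arm. Events are taken as independent.

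**Variance.** Let an arm have N expected events in a class, and let W be its weighted count.

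- Mean of W: N[(1−p) + 2p] = N(1+p). The Poisson model uses this as the variance.
- True variance of W: N[(1−p) + 4p] = N(1+3p).
- Ratio of true to model variance: R = (1+3p)/(1+p).
- Large-count two-sided level: 2[1 − Φ(1.96/√R)].

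**Check against the SAP's figure.** At p = 0, R = 1 and the level is 0.050, as stated. The excess therefore comes from the weights alone.

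**Large-count results.**

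| p | R | level | coverage of nominal 95% interval |
|---|---|---|---|
| 0.05 | 1.095 | 0.061 | 93.9% |
| 0.1 | 1.182 | 0.071 | 92.9% |
| 0.2 | 1.333 | 0.090 | 91.0% |
| 0.5 | 1.667 | 0.129 | 87.1% |
| 1 | 2.000 | 0.166 | 83.4% |

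**Smaller counts.** Simulated with the model's own standard error, 400,000 replicates per cell, p in the same order:

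| events per arm | Wald | likelihood ratio |
|---|---|---|
| 20 | 0.056, 0.065, 0.085, 0.124, 0.165 | 0.063, 0.072, 0.091, 0.130, 0.166 |
| 10 | 0.051, 0.062, 0.080, 0.122, 0.163 | 0.065, 0.076, 0.095, 0.135, 0.174 |
| 3.5 | 0.012 to 0.096 over the range | 0.094 to 0.219 over the range |

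**Coding of the weights.** Three unscaled codings agree: a Poisson fit to each patient's weighted count, and frequency weights or variance weights on arm-by-seriousness records. All three rejected at the same rate, 0.133 at p = 0.5 (1,500 runs, Monte Carlo error about 0.006 to 0.009). Rescaling the weights to mean 1 gives a different answer. Then R = (1+3p)/(1+p)², which peaks at p = 1/3: 2/(16/9) = 1.125. The level there is 2[1 − Φ(1.96/1.061)] = 0.065.

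**Illustration (invented counts).** Take 12 non-serious and 8 serious events against 20 and 15, each in a different patient.

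- Weighted counts: 12 + 16 = 28 and 20 + 30 = 50.
- Log rate ratio: ln(50/28) = 0.580.
- Model SE: √(1/28 + 1/50) = 0.236, so z = 2.46 and two-sided p-value about 0.014.
- Patient-level sandwich SE with 1160 patients per arm: √[(44 − 28²/1160)/28² + (80 − 50²/1160)/50²] = 0.294, so z = 1.97 and p-value about 0.049. Here 44 = 12 + 4×8 and 80 = 20 + 4×15 are the sums of squared weights.

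**After correction.** The patient-level sandwich Wald test, with 20,000 replicates over the p range, has level 0.041–0.045 at 10 events per arm, 0.045–0.049 at 20, 0.048–0.051 at 50 and 0.006–0.027 at 3.5.

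**The case against.** **Silence is not an instruction.** The SAP does not require the model-based standard error, and with a robust or scaled variance the inflation from the weights disappears. This stands as a condition on the finding. It does not remove it: the rule run as written, with nothing added, gives error bars that are too narrow for any p above zero once counts are moderate. Leaving the choice open also leaves the result open, as the two standard errors of 0.236 and 0.294 show.

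**The Type I error statement.** The SAP's Null Hypothesis section says its methods hold the comparison-wise error rate. That sentence concerns outcomes defined only in patients who are on study, and it names no variance. If it is meant to cover adverse events, it fails under the model-based standard error.

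**The serious share may be low.** Protocol 1.2 defines SAEs more narrowly, as serious, unexpected and possibly due to a study procedure. If the doubled weight followed that definition, p would fall. This is fair, and it is why p is shown only as an assumed range.

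**Classes may be sparse.** This also stands. At p = 0.05 the Wald level is about 0.051 at 10 events per arm and 0.056 at 20, which is barely raised. At 3.5 events per arm Wald can be well below 0.05, while the likelihood-ratio test is well above it.

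**Another test may apply.** SAP 1.9 lists adverse events among its additional safety endpoints, so the chi-square or Fisher test for categorical secondary outcomes could be thought to apply too. The dedicated Adverse Events section is the more specific rule, and it is the one assessed here.

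**Conclusion.** The point holds conditionally. With the model's own standard error, unscaled weights and large counts, a nominal 5% class-level test runs at 0.061 to 0.166 for p from 0.05 to 1. The calculation assumes independent events; positive clustering of events within patients would add to the inflation.

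A reader might infer three stronger things that the documents do not support:

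- That these tests will run at about 17%. That needs every event in a class to be serious, and neither the serious share nor the event counts are given.
- That the coding of the weights makes no difference. Rescaling to mean 1 caps the large-count level at 0.065.
- That the trial's main conclusions are at risk. The primary outcome, the stopping boundaries and the separately tested safety endpoints do not use this model.

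Severity is low to moderate. It is worth fixing because the remedy is nearly free.

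**What to change.** Add one sentence to the SAP's Adverse Events section: standard errors, intervals and tests from the weighted Poisson model use a robust (sandwich) variance clustered on patient, with all randomized patients included and those without events contributing zero. The 1 and 2 weights, the Poisson model and the event-based rate ratio stay as they are. The weights then enter the variance squared, and repeat events in one patient are allowed for.

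**Cost.** No new data and a few lines of code. Under independent events, intervals widen by √R − 1: 5%, 9%, 15%, 29% and 41% at p = 0.05, 0.1, 0.2, 0.5 and 1. In very sparse classes the sandwich Wald test is conservative, which costs power to detect harm there.

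**Optional, not part of the required change.** For sparse classes, arm labels could be permuted within institution, since "Randomization will be stratified by the enrolling institution". That test is conservative too: its simulated level is 0.016–0.019 at 3.5 events per arm, assuming 50 sites of unequal size.
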